Information was preferentially taken from documented medical records as preferred means (as it also mentioned the diagnosis associated with OCS administration) or second means, from the pharmacy records (no diagnosis); the third level of certainty was based on information provided by parents to the research coordinator with reports of the drug, posology and diagnosis. However, If self-reported information was not confirmed in the Medical records or Pharmacy report, information on the OCS was reviewed by an independant adjudicator with clinical expertise in asthma.

In the case of multiple exacerbations with OCS use, events were considered separate events if they were separated by 7 days or more. In cases where conflicting information was collected from different sources, or there were multiple reports within a short window of time clinical records were reviewed by the independent adjudicator to determine the number of separate events.

It was considered that there was OCS use if at least one dose of OCS was administered, prescribed or dispensed to the patient. This outcome was chosen because it is a clinically meaningful efficacy measure that has been shown to be important for family, health care providers, and payers, to influence practice, and the metric (counting all OCS per patient) was preferred by parents.

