10.1 What was the reason for SYSTEMIC STEROIDS due to: [phcon_steroid_reas]	1: a. Asthma flare-up 4: b. Asthma-like diagnoses (broncho-spasm, airway hyperreactivity, bronchio-litis, or wheezing) 2: c. Other condition: (record in AHE) 3: d. Unknown	Should not be a missing value
10.1.1 Other condition: [phcon_steroid_4]	text	Should include "bronchospasm, airway hyperactivity, bronchiolitis, bronchitis, wheezing, pneumonia , otitis".
10.2 Medication (Use the generic name(s), NOT trade name(s): (To be documented when interviewing parents, but the generic name MUST be entered before submitting the form): [phcon_steroid_mednam]	1: Prednisone tablet 2: Prednisolone (Pediapred®) 3: Dexamethasone (solution or tablet) 4: Methylprednisolone (solution or tablet) 5: Solucortef 6: Other	Should not be a missing value
10.2a If other, specify: [phcon_steroid_mednam_2]	text	Should not include cefodox / magnesium sulfate / hydrocortisone, other cutaneous, nasal, ophthalmic (etc.) preparation.
10.2.1 Route: [phcon_steroid_medrout]	1: Oral 2: IV 3: IM	Should not be a missing value

10.2.2 mg per dose - - - . _ mg [phcon_steroid_meddos]	text (number)	Should not be a missing value
10.2.3 Frequency (#times/day): [phcon_steroid_medfreq]	1:1 2:2 3:3 4:4	Should not be a missing value
10.2.4 Start date: [phcon_steroid_startdat]	text (date_ymd)	Should not be a missing value
10.2.5 End date: [phcon_steroid_endat]	text (date_ymd)	Should not be a missing value
10.2.6 According to parents, the medication was administered or served by (Both answers are possible) Selon les parents, le médicament a-t-il été administré ou servi par (les deux réponses sont possibles)	[phcon_steroid_servby__1]1: Pharmacy [phcon_steroid_servby__2]1: Hospital	Should not be a missing value
10.2.6.1 Confirmation of dispensing obtained by pharmacy records: If awaiting until the end of study to obtain pharmacy records, leave this question unanswered until then [phcon_sterconfby_pharm]	1: Yes 2: No 3: Pharmacy records never obtained	Should not be a missing value
10.2.6.2 Date of dispensing based on [phcon_sterconfby_pharm_date]	1: Pharmacy records 2: Credible report by parents of an alternate start date than that documented in pharmacy records (for example, medication dispensed ahead of time for subsequent use as part of an action plan) 3: Credible report by parents of denied administration of prescribed or dispensed 4: Unconfirmed as pharmacy	Should not be a missing value

	records NEVER obtained	

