8.1.1 What was the reason for SYSTEMIC STEROIDS due to: [acafu_steroid_reas]	1a. Asthma flare-up, specify episode # below 2b. Asthma-like diagnoses (bronchospasm, airway hyperreactivity, bronchiolitis, bronchitis, wheezing, or pneumonia) 3c. Other condition: (record in AHE) 4d. Unknown	Should not be a missing value

8.1.1.1 Other condition: [acafu_steroid_oth]	text	Should include “bronchospasm, airway hyperactivity, bronchiolitis, bronchitis, wheezing, pneumonia , otitis”.
8.1.2 Medication (Use the generic name(s), NOT trade name(s): (To be documented when interviewing parents, but the generic name MUST be entered before submitting the form): [acafu_steroid_mednam]	1Prednisone tablet 2Prednisolone (Pediapred®) 3Dexamethasone (solution or tablet) 4Methylprednisolone (solution or tablet) 5Solucortef 6Other	Should not be a missing value
8.1.2.1 If other, specify: [acafu_steroid_mednam_oth]	text	Should not be a missing value
8.1.3 Route: [acafu_steroid_medrout]	1Oral 2IV 3IM	Should not be a missing value
8.1.4 mg per dose: [acafu_steroid_meddos] _____.____mg	text (number)	Should not be a missing value
8.1.5 Frequency (#times/day): [acafu_steroid_medfreq]	11 22 33 44	Should not be a missing value
8.1.6 Start date: [acafu_steroid_startdat]	text (date_ymd)	Should not be a missing value
8.1.7 End date: [acafu_steroid_endat]	text (date_ymd)	Should not be a missing value
8.1.8 According to parents, the medication was administered or served by (Both answers are possible)	acafu_steroid_servby____1: Pharmacy: 1 acafu_steroid_servby____2: Hospital: 1	Should not be a missing value
8.1.8.1 Confirmation of dispensing obtained by pharmacy records: [acafu_sterconfby_pharm]	1Yes 2No 3Pharmacy records never obtained	Should not be a missing value

8.1.8.2 Date of dispensing based on: [acafu_stecnfby_pharm_date]
	
1Pharmacy records 2Credible report by parents of an alternate start date than that documented in pharmacy records (for example, medication dispensed ahead of time for subsequent use as part of an action plan) 3Credible report by parents of denied administration of prescribed or dispensed 4Unconfirmed as pharmacy records NEVER obtained
	
Should not be a missing value

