
8.1.8.3 Confirmation of administration with/without dispensing obtained from hospital: [acafu_stercnfby_hosp] If awaiting until the end of study to obtain hospital/clinic records, leave this question unanswered until then
	
1Yes 2No 3Hospital/clinic Records NEVER obtained
	
Should not be a missing value

8.1.8.4 Date of administration/dispensing confirmation based on: [acafu_stecnfby_hosp_date]
	
1Hospital/clinic records 2Credible report by parents of an alternate start date (for example, medication dispensed ahead of time for subsequent use as part of an action plan) 3Credible report by parents of denied administration of prescribed or dispensed medication 4Unconfirmed as hospital/clinic records NEVER obtained
	
Should not be a missing value

Comment: the same coding should be applied to Q8.2 – Q8.5.

Variable / Field Name / Field Label	Field Attributes (Field Type, Validation, Choices)	Required
1. Has there been any administration and/or prescription of systemic (oral, IM, IV) corticosteroids (OCS*) documented in the medical record for asthma or asthma-like symptoms since randomization until V3 (or 7 months after randomization if premature discontinuation) ? [ocsdःdoc_end_syst_yn]	1Yes 0No	Should be Yes
Was the OCS: (choose all that apply)	ocsdःdoc_end_syst_y_1 1:administrated (or given to patient) ocsdःdoc_end_syst_y_2 1: prescribed (to be filled by community pharmacy)	Should not be a missing value
1.1.1 Date of administration (1st dose) [ocsdःdoc_end_adm_date]	text (date_ymd), Required	Should not be a missing value
1.1.2 Medication (use the generic or trade name) [ocsdःdoc_end_med]	1Prednisone tablet 2Prednisolone (pediapred) 3Dexamethasone (solution or tablet) 4Methylprednisolone (solution or tablet) 5Other	Should not be a missing value
1.1.2 a) If other, specify[ocsdःdoc_end_med_oth]	text	Should not include hydrocortisone or other unrelated medications
1.1.3 Route[ocsdःdoc_end_route]	1Oral 2IV 3IM	Should not be a missing value
1.1.4 mg per dose[ocsdःdoc_end_mg] mg	text, Required	Should not be a missing value
1.1.5 What was the reason for	1a) Asthma flare-up	Should not include

SYSTEMIC STEROIDS due to: [ocsdoc_end_reason]	2b) Asthma-like symptoms: bronchospasm, airway hyperactivity, bronchiolitis, bronchitis, wheezing, pneumonia 3c) Laryngitis 4d) Unknown	Laryngitis

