1.1.6 Total number of doses administered or given to parents by health care provider (for example include a dose of dexamethasone to give at home by parents) [ocsdoc_end_nb_dos] # doses	text	Should not be a missing value
1.1.7 Was the dose accompanied by a prescription (to be filled by community pharmacy), as documented in the medical chart? [ocsdoc_end_pres]	1Yes 0No	Should not be a missing value
1.1.7.1 Date of prescription[ocsdoc_end_pres_date]	text (date_ymd), Required	Should not be a missing value
1.1.7.2 Medication (Use the generic name(s), NOT trade name(s)): [ocsdoc_end_pres_med]	1Prednisone tablet 2Prednisolone (Pediapred®) 3Dexamethasone (solution or tablet) 4Methylprednisolone (solution or tablet) 5Solu cortef 6Other	Should not be a missing value
1.1.7.2 a) If other, specify[ocsdoc_end_pres_med_oth]	text	Should not include hydrocortisone or other unrelated medications
1.1.7.3 Route[ocsdoc_end_pres_route]	1Oral 2IV 3IM	Should not be a missing value
1.1.7.4 Total daily dose in mg[ocsdoc_end_pres_tot_mg]	text	Should not be a missing value

mg		
1.1.7.5 Prescription duration (# days) [ocsdoc_end_pres_dur] days	text	Should not be a missing value

Comment: the same coding should be applied to information about Medication 2 (Q1.2.1 - Q1.2.7.5) and Medication 3 (Q1.3.1 - Q1.3.7.5).

Pharmacy Report / End of Study CRF

Variable / Field Name / Field Label	Field Attributes (Field Type, Validation, Choices)	Required
Section Header: Oral Corticosteroids (OCS) Medication	1 Yes 0 No	Should be Yes
1. Has there been any serving of oral corticosteroids (OCS) medication since randomization until V3 (or 7 months after randomization if premature discontinuation) ? [pharm_ocs_end]		
1.1.1 Date of dispensing [pharm_ocs_end_dat_disp_1]	text (date_ymd), Required	Should not be a missing value
1.1.2 Medication (use the generic or trade name) [pharm_ocs_end_nam_1]	1 Prednisone tablet 2 Prednisolone (pediapred) 3 Dexamethasone (solution or tablet) 4 Methylprednisolone (solution or tablet) 5 Other (specify DIN)	Should not be a missing value
1.1.2 a) Specify [pharm_ocs_end_nam_1a]	text	Should not include hydrocortisone or other unrelated medications

1.1.4 mg per dose [pharm_ocs_end_dos_1] mg	text, Required	Should not be a missing value
1.1.5 Frequency (#times/day) [pharm_ocs_end_freq_1] #times/day	text	Should not be a missing value
1.1.6 Prescription duration (#days) [pharm_ocs_end_dur_1] days	text	Should not be a missing value

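### Appendix 1 accepts Solu-Cortef on some items and screens out hydrocortisone on others, so whether a dose counts towards the primary outcome can depend on where and how it was entered

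*SAP*

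**What the plan says.** The SAP's Primary outcome section ranks the sources. Medical records come first ("Information was preferentially taken from documented medical records as preferred means"), pharmacy records second and parental report third. A single dose given, prescribed or dispensed is enough for an event. The manuscript wording suggested at the start of Appendix 1 defines the outcome as short courses of systemic corticosteroids prescribed for asthma.

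Appendix 1 then tabulates the drug fields form by form, with a *Required* column giving the condition each field should meet. Three medication lists include Solu-Cortef as a coded choice:

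- Visit and Phone Contact, item 10.2: "4: Methylprednisolone (solution or tablet) 5: Solucortef 6: Other"
- Additional Cold or Asthma Flare-up, item 8.1.2: "4Methylprednisolone (solution or tablet) 5Solucortef 6Other"
- OCS in medical records at end of study, prescription item 1.1.7.2: "5Solu cortef 6Other"

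The hospital-administered item of the medical-record form (1.1.2) lists four steroids and *Other*. The free text for *Other* (1.1.2 a) carries the condition "Should not include hydrocortisone or other unrelated medications". The same condition stands at Medical Examination item 9.1, prescription item 1.1.7.2 a and Pharmacy Report item 1.1.2 a. Item 10.2a of the Visit and Phone Contact form has a related one: "Should not include cefodox / magnesium sulfate / hydrocortisone, other cutaneous, nasal, ophthalmic (etc.) preparation".

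**The concern.** Solu-Cortef is a trade name for hydrocortisone. The SAP does not say so, but this is ordinary drug naming. The same drug is therefore an accepted entry in some places and an unacceptable one in others, within the coding of the primary outcome.

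The hospital-administered item matters most. It is part of the SAP's preferred source, and it offers no route by which the drug can be entered and pass. An exacerbation treated in the emergency department or on a ward with IV hydrocortisone is within the form's declared scope, yet its record meets a check that names the drug as one that should not be there. Two analysts could reasonably code such a record differently, or could both drop an event that the outcome definition would count.

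**Working it through.** No arithmetic in the plan is at issue. The check compares the drug fields of Appendix 1 item by item.

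| Form and item | Solu-Cortef has its own code | Check on *Other* free text |
|---|---|---|
| Visit and Phone Contact, 10.2 and 10.2a | Yes | Hydrocortisone should not appear (named beside topical products) |
| Additional Flare-up, 8.1.2 and 8.1.2.1 | Yes | Only that the field is not missing |
| Medical Examination, 9 a) and 9.1 | No | Hydrocortisone should not appear |
| Medical records, administered, 1.1.2 and 1.1.2 a) | No | Hydrocortisone should not appear |
| Medical records, prescribed, 1.1.7.2 and 1.1.7.2 a) | Yes | Hydrocortisone should not appear |
| Pharmacy Report, 1.1.2 and 1.1.2 a) | No | Hydrocortisone should not appear |

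Three of the six items accept the drug by code and five of the six screen it out as free text. Items 10.2 and 1.1.7.2 do both. These two items also ask for generic names, so a coordinator who types hydrocortisone under *Other* fails the check, while one who ticks the Solu-Cortef code passes.

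**Does the check at 1.1.2 a) reach systemic asthma doses?** The form's opening question is limited to oral, IM or IV corticosteroids for asthma or asthma-like symptoms, and the route field offers only those three routes. A topical product has no valid place there, so a hydrocortisone entry that belongs on the form is systemic. Under *Relationship with an asthma exacerbation*, Appendix 1 excludes courses by reason (for example adrenal insufficiency or croup), not by drug. The wording at 10.2a suggests that topical products were the target, but 1.1.2 a) carries no such limit.

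**Tracing one exacerbation treated with IV hydrocortisone**

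1. Coded as Solu-Cortef on a parent-report form: passes.
2. Coded as Solu-Cortef under prescription item 1.1.7.2: passes.
3. Hospital-administered entry plus another listed steroid in the same episode: the event is kept, because courses starting within 7 days count once.
4. Hospital-administered entry plus a parent report: the parent record passes. It may carry hospital confirmation (items 10.2.6.3 and 8.1.8.3) or go to the adjudicator.
5. Hospital-administered entry only: it fails the check and nothing else keeps the event.

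**Do the safeguards reach case 5?** Adjudication is triggered by an unconfirmed parental report, by conflicting or closely spaced reports, by a course on the day of randomisation, or by a rule on which the two biostatisticians' coding differs. A lone hospital entry on a later day meets none of the first three. If both coders apply the written check in the same way, there is no discrepancy either.

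**Size.** The SAP gives no event total and no drug distribution. As an illustration only, assume 300 events in total, with hydrocortisone the sole recorded systemic steroid in 0.5% to 2% of them. Then 300 × 0.005 = 1.5 and 300 × 0.02 = 6, or about 2 to 6 events. Case 5 is a subset of these, because some will also have a parent report.

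**The case against.** The strongest reply is that the *Required* column is a data check and not an exclusion rule. Appendix 1 introduces its variable list as including conditions to verify. Most entries in the column ask only that the field is not missing, and a comment under the Visit and Phone Contact table allows missing values to be imputed, so failing a condition is not automatic removal. The explicit exclusions under *CRF specific coding rules* are by reason, and none is by drug name. This stands as a limit: loss of the event is conditional on how the check is used. It does not settle the matter, because the parallel entry for laryngitis in the same column does correspond to an explicit exclusion, and the SAP gives no instruction on what to do with a flagged drug.

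A reader might infer that parent-report forms accept the drug while the hospital form rejects it. The documents do not support that. The Visit and Phone Contact form screens hydrocortisone as free text, and the medical-record form accepts Solu-Cortef as a prescription. The conflict is between items.

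A reader might also infer that a hospital-treated event survives only if a parent names the drug. That is too strong: a listed steroid in the same episode, item 1.1.7.2, the hospital-confirmation fields and adjudication can each preserve it.

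Finally, a drug-name screen is easier to defend on the pharmacy form, which asks about oral products and does not give the reason for prescription. That argues for a rule that uses route and reason where they exist, not for leaving item 1.1.2 a) as it is.

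**Conclusion.** The inconsistency is in the text and bears on the primary-outcome count. The clear loss is narrow: an event documented only by a hospital-administered entry of hydrocortisone, with the check applied as an exclusion. A second, smaller problem is that the generic name typed as free text can fail where the trade-name code passes.

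The number of events affected is unknown and probably small; the 2 to 6 above rests wholly on assumed inputs. A reader might go on to infer a biased treatment comparison. The documents do not show one, since the same check applies to both blinded arms. What is at stake is the completeness and reproducibility of the count, for hospital-treated exacerbations within the SAP's preferred source. The point is worth correcting because the correction is specific and nearly free.

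**What to change.** Before unblinding, reconcile items 10.2a, 9.1, 1.1.2 a), 1.1.7.2 a) and the pharmacy item 1.1.2 a), together with the coded lists at 10.2, 8.1.2 and 1.1.7.2, into one drug rule for all sources.

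- Base the rule on recorded route and reason where the form holds them, consistent with Appendix 1's definition in terms of systemic corticosteroids and with its reason-based exclusions.
- If the hydrocortisone screen was meant for topical products, limit it to non-systemic preparations and say so. Which drugs qualify is for the sponsor to state, once, for every form.
- State whether failing a *Required* drug condition excludes a record or only flags it.
- Recode the *Other* free text under that rule, treating generic and trade names alike.
- Send any hospital record flagged by the drug check to the independent adjudicator.

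The cost is a short change to the SAP wording, one recode of existing free-text entries and probably only a few adjudications. No new data are needed.

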Appendix 2: Secondary Outcome coding

Number of laboratory-confirmed respiratory infections per child

1. **Timing:** exacerbations documented in REDCap after the Randomization over the period of study follow-up will be considered.
 - 1.1. Nasal swabs collected during Clinic Visit 1 – to be disregarded
 - 1.2. Nasal swabs collected during Clinic Visit 2, CRF “Nasal swab (clinic)”:
 - If routine swab collection and no exacerbation reported (Q1. According to parents, is the child sick (cold or asthma)? = “No”) – to be disregarded;
 - If exacerbation reported “Q1. According to parents, is the child sick (cold or asthma)? = “Yes” – included in calculation;
 - 1.3. The swabs collected by parents at home during cold or exacerbations and documented in the CRF “Nasal swab reception (from parents)”, brought back at Clinic Visit 2 and Clinic Visit 3 - to be included in calculations;
2. **Lab results** will be provided by McMaster Lab, the xlsx file with the data and the codebook will be uploaded directly to the URCA OwnCloud.
3. The **biobank log**, showing the correspondence between the nasal swabs collected/received and lab results provided by McMaster Lab is managed by the Study Coordination Centre.

List of viruses to explore/report:

1. Rhino/Enteru_Result
2. InfluenzaA_Result
3. InfluenzaB_Result
4. Parainfl1_Result
5. Parainfl2_Result
6. Parainfl3_Result
7. HMPV_Result
8. RSV_Result
9. Adeno_Result
10. SARS-CoV2_Result

Number of ED or acute-care visits / hospital admissions

Number of reported and/or documented ED or acute –care visits and hospitalisations for asthma and asthma-like diagnosis, obtained throughout the 7-month study period from:

REDCap – verbal parental report:

- Visit and Phone contact CRF (9 timepoints, self-reported, completed by Coordinator);
 - Q 3. Did the flare-up result in an UNSCHEDULED visit to an acute care centre due to respiratory difficulty (includes pneumonia, asthma)? – up to Q 3.4.1;
 - Q 3.5 Was the subject admitted to the hospital? – up to Q 3.5.4a;
 - Q 4. Did the flare-up result in any other UNSCHEDULED visit to an acute care centre due to respiratory difficulty (includes pneumonia, asthma)? – up to Q 4.4.1;
 - Q 4.5 Was the subject admitted to the hospital? – up to Q 4.5.5.4a;
- Additional Cold or Asthma Flareup CRF (As needed, self-reported, completed by Coordinator); (the same structure as VPC CRF, Q 3, Q 3.5, Q 4, Q4.5)

REDCap3 – written parental report:

- Summary of an asthma flare-up or cold (REDCap3, final summary CRF for each episode) completed by parents at the end of each the episode:
 - **Section:** Was your child taken to the Emergency Department or any other acute care facility? [sum_emerg_yn] – up to Q [sum_emerg_doctor_autre_2];
 - **Section:** Was your child hospitalized (which implies leaving the emergency room for another hospital unit)? [sum_hospit_yn].

Of note, coordinators were instructed to check medical records and parents' summary of an asthma flare-up or cold, at the end of the follow-up to identify any acute care centre visit or hospitalization for asthma or asthma-related diagnosis and recorded it in VPC; the distribution of the means of confirmation of the event (Q3.4.1; 4.4.1) will be described. In addition to serving to confirm the diagnosis at such visit, this systematic verification at the end of the follow-up (or 7 months in case of drop-outs or loss to follow-up) was intended to maximise the documentation of all events, to avoid

omission or data loss due to study discontinuation prior to Visit 3.

Treatment intensification at Visit 2 & 3

Treatment intensification (vs. no change or treatment de-intensification) at V2 (3.5 months) and V3 (7 months) time points is reported by the treating physician. Intensification is defined as an increase in the total daily dose of ICS of more than 50 ug/day, the addition of an additional daily preventive drug, or an increase of more than 200 ug/day in the dose of ICS given pre-emptively at the onset of an exacerbation.

To identify any deterioration, the asthma controller regimen prescribed in detail at each visit was categorized by the treating physician in representing

- A treatment intensification defined as an increase in the TOTAL daily DOSE of ICS of >50 ug/day OR the ADDITION of another daily preventive drug OR an INCREASE >200 ug/day in the dose of ICS given pre-emptively at onset of exacerbation
- NO substantial change OR
- A treatment deintensification defined as decrease in the TOTAL daily DOSE of ICS of >50 ug/day OR the CESSATION of another daily preventive drug OR a DECREASE >200 ug/day in the dose of ICS given pre-emptively at onset of exacerbation.

REDCap Codebook:

[medex_best_opt_man_2] At Visit 2 and Visit 3:

10. Compared to the last visit, today's recommendations represent (record the best option):

- 1: no substantial change;
- 2: a treatment intensification;
- 3: a treatment desintensification.

